1.9 Rationale

One main limitation to the widespread use of contrast enhanced ultrasound clinically has been the lack of availability of state-of-the art contrast imaging approaches available to clinicians. However, contrast ultrasound will likely become far more widespread as new imaging techniques, such as CESR imaging, demonstrate their usefulness and become available on commercial ultrasound systems. We propose to evaluate a novel ultrasound method that could potentially improve the sensitivity and specificity of traditional breast and thyroid ultrasound. Increasing the accuracy of diagnostic imaging in high risk patients could provide substantial clinical benefit by improving diagnosis, preventing over-treatment, and reducing healthcare costs.

LCCC1915 is designed to evaluate the sensitivity and specificity of contrast enhanced super-resolution ultrasound imaging in the analysis of known breast and thyroid lesions in patients with pathologically confirmed diagnoses of breast or thyroid cancer compared with pre-study imaging results. The gold standard for sensitivity and specificity, then, will be based on pathological results. The Breast Imaging Reporting and Data System (BIRADS) is used by radiologists who read mammograms, ultrasounds, and MRIs to indicate their level of suspicion of the possibility of breast cancer. Scores range from 0 to 6, with scores of 4-5 indicating suspicious results, while 6 indicates an existing diagnosis of breast cancer. For the breast cohort, this study is limited to women with a score of 4-5 based on pre-study imaging. We selected this group of patients because there is more likely to be a cancer diagnosis than BIRADS 1-3.

For the thyroid cohort, we will include patients scheduled for a core needle or surgical thyroid biopsy, fine needle aspiration, or thyroidectomy of at least one sonographically visible thyroid lesion that is 3 cm in depth from the skin surface. We will recruit patients with high TIRADS risk scores (4c, moderately suspicious and 5, high risk), that have an anticipated risk range of 50% to in excess of 85%, which will provide an estimated relative risk of 75% to be congruent with the breast population.

2.0 STUDY OBJECTIVES

2.1 Primary Objectives

- 2.1.1** To evaluate the sensitivity and specificity of contrast enhanced super-resolution imaging in the analysis of known breast lesions by comparing image analyses to the pathological results for these lesions.
- 2.1.2** To evaluate the sensitivity and specificity of contrast enhanced super-resolution imaging in the analysis of known thyroid lesions by comparing image analyses to the pathological results for these lesions.

2.2 Secondary Objectives

- 2.2.1** To compare (using a reader study) the sensitivity and specificity of contrast enhanced super-resolution imaging to the sensitivity and specificity of conventional b-mode ultrasound in evaluation of known breast lesions for predicting malignancy.
- 2.2.2** To compare (using a reader study) the sensitivity and specificity of contrast enhanced super-resolution imaging to the sensitivity and specificity of conventional b-mode ultrasound in evaluation of known thyroid lesions for predicting malignancy.
- 2.2.3** To compare the area under the curve (AUC) of contrast enhanced super-resolution imaging to the AUC of the b-mode ultrasound.
- 2.2.4** To compare radiologist preference of contrast enhanced super-resolution imaging to conventional b-mode ultrasound for each lesion characteristic (shape, margins, and vascularity).

2.3 Endpoints

We will utilize pathological status as derived from patient biopsy pathology reports.

3.0 PATIENT ELIGIBILITY

3.1 Arm 1: Healthy Volunteers

3.1.1 Inclusion Criteria

Subject must meet all of the inclusion criteria to participate in this study:

3.1.1.1 Adults ≥ 18 years old

3.1.1.2 Able to provide informed consent

3.1.1.3 Negative urine pregnancy test in women of child-bearing potential

3.1.2 Exclusion Criteria

All subjects meeting any of the exclusion criteria at baseline will be excluded from study participation

3.1.2.1 Institutionalized subject (prisoner or nursing home patient)

3.1.2.2 Critically ill or medically unstable and whose critical course during the observation period would be unpredictable (e.g., chronic obstructive pulmonary disease (COPD))

3.1.2.3 Known hypersensitivity to sulfur hexafluoride or to any component of perflutren lipid (Definity®)

3.1.2.4 Active cardiac disease including any of the following:

- Severe congestive heart failure (class IV in accordance with the classification of the New York Heart Association)
- Unstable angina.
- Severe arrhythmia (i.e. ventricular tachycardia, flutter fibrillation; ventricular premature complexes occurring close to the preceding T-wave, multifocal complexes).
- Myocardial infarction within 14 days prior to the date of proposed Definity® administration.
- Pulmonary hypertension
- Cardiac shunts

3.1.2.5 Any woman who is pregnant or has reason to believe she is pregnant or any woman who is lactating (the possibility of pregnancy has to be excluded by negative urine β -HCG results, obtained within 24 hours before the perflutren lipid administration, or on the basis of patient history, as defined by the UNC IRB SOP 4801.)

3.2 Arm 2: Breast Imaging Patients

3.2.1 Inclusion Criteria

Subject must meet all of the inclusion criteria to participate in this study:

3.2.1.1 Women ≥ 18 years old

3.2.1.2 Patient had a diagnostic breast ultrasound study performed at UNC

3.2.1.3 Scheduled for a core needle or surgical breast biopsy of at least one breast lesion that is 2 cm or less in size and 3 cm in depth from the skin surface

3.2.1.4 Lesion visualized on ultrasound

3.2.1.5 Able to provide informed consent

3.2.1.6 Negative urine pregnancy test in women of child-bearing potential

3.2.1.7 BIRADS score of 4 or 5.

3.2.2 Exclusion Criteria

All subjects meeting any of the exclusion criteria at baseline will be excluded from study participation

3.2.2.1 Male (it is uncommon for men to present for imaging and the overwhelming majority of findings are non-cancerous and do not lead to biopsy; male breast cancer represents <1% of newly diagnosed breast cancer)

3.2.2.2 Institutionalized subject (prisoner or nursing home patient)

3.2.2.3 Critically ill or medically unstable and whose critical course during the observation period would be unpredictable (e.g., chronic obstructive pulmonary disease (COPD))

3.2.2.4 Sonographically visible breast lesion larger than 2cm or greater than 3cm in depth from the skin surface

3.2.2.5 Known hypersensitivity to sulfur hexafluoride or to any component of perflutren lipid (Definity®)

3.2.2.6 Active cardiac disease including any of the following:

- Severe congestive heart failure (class IV in accordance with the classification of the New York Heart Association)
- Unstable angina.
- Severe arrhythmia (i.e. ventricular tachycardia, flutter fibrillation; ventricular premature complexes occurring close to the preceding T-wave, multifocal complexes).
- Myocardial infarction within 14 days prior to the date of proposed Definity® administration.
- Pulmonary hypertension
- Cardiac shunts

3.2.2.7 Any woman who is pregnant or has reason to believe she is pregnant or any woman who is lactating (the possibility of pregnancy has to be excluded by negative urine β-HCG results, obtained within 24 hours

before the perflutren lipid administration, or on the basis of patient history, as defined by the UNC IRB SOP 4801.)

3.3 Arm 3: Thyroid Imaging Patients

3.3.1 Inclusion Criteria

Subject must meet all of the inclusion criteria to participate in this study:

- 3.3.1.1 Adults \geq 18 years old
- 3.3.1.2 Patient had a diagnostic thyroid ultrasound study performed at UNC
- 3.3.1.3 TIRADS risk score of 4c or 5
- 3.3.1.4 Scheduled for a core needle or surgical thyroid biopsy, fine needle aspiration, or thyroidectomy of at least one sonographically visible thyroid lesion that is 3 cm in depth from the skin surface
- 3.3.1.5 Lesion visualized on ultrasound
- 3.3.1.6 Able to provide informed consent
- 3.3.1.7 Negative urine pregnancy test in women of child-bearing potential

3.3.2 Exclusion Criteria

All subjects meeting any of the exclusion criteria at baseline will be excluded from study participation

[figure not shown]
- 3.3.2.1 Institutionalized subject (prisoner or nursing home patient)
- 3.3.2.2 Critically ill or medically unstable and whose critical course during the observation period would be unpredictable (e.g., chronic obstructive pulmonary disease (COPD))
- 3.3.2.3 Known hypersensitivity to sulfur hexafluoride or to any component of perflutren lipid (Definity®)
- 3.3.2.4 Active cardiac disease including any of the following:
 - Severe congestive heart failure (class IV in accordance with the classification of the New York Heart Association)
 - Unstable angina.
 - Severe arrhythmia (i.e. ventricular tachycardia, flutter fibrillation; ventricular premature complexes occurring close to the preceding T-wave, multifocal complexes).
 - Myocardial infarction within 14 days prior to the date of proposed Definity® administration.
 - Pulmonary hypertension
 - Cardiac shunts

3.3.2.5 Any woman who is pregnant or has reason to believe she is pregnant or any woman who is lactating (the possibility of pregnancy has to be excluded by negative urine β -HCG results, obtained within 24 hours before the perflutren lipid administration, or on the basis of patient history, as defined by the UNC IRB SOP 4801.)

4.0 STUDY PLAN

4.1 STUDY SCHEMA

This is a 3-arm single center study of 45 patients scheduled to undergo a breast or thyroid biopsy that consent to undergo a CESR scan in conjunction with b-mode ultrasound prior to their scheduled biopsy.

¹Pre-ultrasound contrast agent

²Based on results of pre-study imaging

Figure 1. Study schema.

4.2 Study Procedures

Study participants will be enrolled for 1 research imaging visit. In addition, their medical charts will be followed for 6 months.

4.2.1 Enrollment/Recruitment

A total of 45 adults will be enrolled to this study. The study subjects will be consecutively recruited from adults who are scheduled to undergo core needle or surgical biopsy to have pathological confirmation of malignancy status. Eligible patients will be identified by research staff review.

Once a patient has been referred, the patient will be approached by a coordinator from Radiology to assess interest in participation.

All eligible subjects who agree to participate in the study will be asked to come to their scheduled biopsy appointment thirty minutes early to complete the informed consent process.

Review of the consent will take place in the privacy of an exam room, or when possible, a sample consent form will be sent to the patient via email prior to the patient's visit to allow for ample review. Once the patient has consented, women of childbearing potential (WCBP) will be given a urine pregnancy test in order to ensure that they are not pregnant. If a urine pregnancy test shows a result positive for pregnancy, the patient will be excluded from the study per the exclusion criteria because the investigators cannot, in good conscience, expose a fetus to the contrast agent used. Women who consent for the study and are eligible will be escorted by the research coordinator to a dressing room, where the subject will change into a gown.

4.2.2 Research Imaging

4.2.2.1 Contrast Administration (if applicable)

At the time of imaging, the contrast agent perflutren lipid will be administered. See <https://definityimaging.com/using-definity> for instructions on perflutren lipid preparation and activation. Perflutren lipid is intended for intravenous (IV) administration only after activation in the Vialmix® apparatus. Cardiopulmonary resuscitation personnel and equipment will be readily available prior to perflutren administration, and all patients will be monitored for acute reactions.

Monitoring will include taking vitals (O₂ sat, HR, RR, BP). Vitals will first be collected at arrival to the clinic. All patients will be visually monitored for signs or symptoms of a contrast administration reaction once the drug is administered for a 15-minute period. Once 15 minutes have passed, vitals will be taken again. This study will be conducted in Mammography of the UNC Cancer Hospital, so trained medical personnel will be available as needed.

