Following a meeting of the FDA Cardio-renal Advisory Committee in 2008, the black box warning was revised. The revisions shortened the contraindications to include cardiac shunts and hypersensitivity to perflutren, and mandated the 30 minute monitoring period be limited to patients with pulmonary hypertension or unstable cardiopulmonary conditions. The black box warning was further revised in 2011, removing the mandatory 30 minute monitoring period, but stating that most serious cardiopulmonary reactions occur within 30 minutes of administration. For this reason, the label states that cardiopulmonary resuscitation personnel and equipment be readily available prior to perflutren administration, and that all patients be monitored for acute reactions.

Patients with a history of cardiac shunts, pulmonary hypertension or unstable cardiopulmonary conditions will be excluded from our study. In addition, all patients will be monitored for 15-minute post-perflutren administration by the research nurse or research physician.

Hypersensitivity Reactions

The real risk of perflutren in our study is to the small number of potential patients with undiagnosed allergy to perflutren. Post-marketing reports have included anaphylactoid events and other serious but non-fatal adverse reactions, typically within 30 minutes of drug administration (see the package insert for additional information. In order to avoid a potentially fatal event, epinephrine will be readily accessible in the code cart in the mammography clinic.

High Ultrasound Mechanical Index (MI)

High ultrasound MI values may cause microsphere cavitation or rupture and lead to ventricular arrhythmias. In addition, end-systolic triggering with high mechanical indices has been reported to cause ventricular arrhythmias.

Use in Patients with Known Breast Lesions

US contrast agents including perflutren should carry no additional risks in patients with a known breast lesions, as they are cleared by the lungs. The phospholipid component of perflutren lipid microspheres are thought to be metabolized to free fatty acids, while the octafluoropropane (OFP), as a stable gas, is not metabolized. In a small (n=8) pharmacokinetic study in healthy subjects, OFP was undetectable after 10 minutes in most subjects either in the blood or expired air, with a mean half-life of 1.3 minutes (Definity® Prescribing Information).

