4.2.2.2 Imaging Procedures

CESR imaging involves a research ultrasound scanner as well as conventional b-mode ultrasound to guide the location of the imaging. The conventional ultrasound will be conducted just prior to CESR imaging for localization. Imaging will be performed within the package insert guidelines for ultrasound system mechanical index (a measurement of output power) when imaging perflutren contrast agent (less than 0.8).

CESR imaging will be performed by trained medical personnel using mild compression to eliminate motion. Total imaging time is estimated to be less than 15 minutes. All image data will be de-identified and transferred for off-line analysis based on a study ID. The research images will NOT be interpreted or analyzed for clinical decisions related to the patient. The field of view of the research images will be limited to clinically identified

lesions. Incidental findings are not anticipated due to the sensitivity limitations of this imaging modality. Information regarding additional lesions or other incidental findings discovered during research imaging procedures will not be recorded or communicated to the patient or their provider because this imaging modality is not standard of care.

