6.1.1 Known and Associated Risks

For indication see <https://www.definityimaging.com/pdf/definity-pi.pdf> and see section 1.8.2 for a summary of toxicities reported in clinical trials. In addition, the following warnings and precautions are noted in the January 2017 labeling:

Serious Cardiopulmonary Reactions:

Serious cardiopulmonary reactions including fatalities have occurred uncommonly during or shortly following perflutren-containing microsphere administration, typically within 30 minutes of administration. The risk for these reactions may be increased among patients with unstable cardiopulmonary conditions (acute myocardial infarction, acute coronary artery syndromes, worsening or unstable congestive heart failure, or serious ventricular arrhythmias). Always have cardiopulmonary

resuscitation personnel and equipment readily available prior to Definity® administration and monitor all patients for acute reactions. The reported reactions include: fatal cardiac or respiratory arrest, shock, syncope, symptomatic arrhythmias (atrial fibrillation, tachycardia, bradycardia, supraventricular tachycardia, ventricular fibrillation, ventricular tachycardia), hypertension, hypotension, dyspnea, hypoxia, chest pain, respiratory distress, stridor, wheezing, loss of consciousness, and convulsions.

Hypersensitivity Reactions:

In postmarketing use, serious hypersensitivity reactions were observed during or shortly following perflutren-containing microsphere administration including: Shock, bronchospasm, throat tightness, angioedema, edema (pharyngeal, palatal, mouth, peripheral, localized), swelling (face, eye, lip, tongue, upper airway), facial hypoesthesia, rash, urticaria, pruritus, flushing, and erythema have occurred in patients with no prior exposure to perflutren-containing microsphere products. Always have cardiopulmonary resuscitation personnel and equipment readily available prior to Definity® administration and monitor all patients for hypersensitivity reactions.

Systemic Embolization of Perflutren in Patients with Cardiac Shunts:

When administering Definity® to patients with a cardiac shunt, the microspheres can bypass filtering by the lung and enter the arterial circulation. Assess patients with shunts for embolic phenomena following Definity® administration. Definity® is only for intravenous administration; do not administer Definity® by intra-arterial injection.

Ventricular Arrhythmia Related to High Mechanical Index:

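### Specified reaction monitoring stops 15 minutes after perflutren, while the protocol places most serious reactions within 30 minutes and does not justify the shorter period

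*Combined protocol and SAP*

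**What the plan says.** **Monitoring.** Section 4.2.2.1 sets the observation: "All patients will be visually monitored for signs or symptoms of a contrast administration reaction once the drug is administered for a 15-minute period". It continues: "Once 15 minutes have passed, vitals will be taken again". Section 1.8.2 agrees: "all patients will be monitored for 15-minute post-perflutren administration by the research nurse or research physician".

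**Timing of serious reactions.** The protocol gives a 30-minute figure three times:
- Section 1.8.2, on the 2011 label revision: "most serious cardiopulmonary reactions occur within 30 minutes of administration".
- Section 1.8.2, on post-marketing anaphylactoid and other serious non-fatal reactions: "typically within 30 minutes of drug administration".
- Section 6.1.1, on serious cardiopulmonary reactions in the 2017 labeling: "typically within 30 minutes of administration".

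**Context.** Section 1.8.2 reports that the 2011 revision removed the mandatory 30-minute monitoring period. It then gives the 30-minute timing as the label's reason for requiring resuscitation cover and monitoring of all patients for acute reactions, with no duration attached. It excludes patients with cardiac shunts, pulmonary hypertension or unstable cardiopulmonary conditions, and it identifies undiagnosed perflutren allergy as the real risk in this study.

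**The concern.** The protocol gives one interval for when serious reactions tend to occur and another, half as long, for how long it will look for them. It does not connect the two. Anyone following section 4.2.2.1 as written may end specified reaction monitoring, and take the last vitals, midway through the interval that section 1.8.2 uses to explain why monitoring is needed.

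What is at stake is prompt recognition of a rare but potentially fatal reaction. Breast and thyroid patients go straight to their scheduled procedure (section 4.2.3), with no reaction monitoring specified during it. Healthy volunteers have no such procedure, and the protocol describes nothing for them after imaging.

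**Working it through.** The plan has no figure of its own to reproduce here, so the check is a comparison of sections plus two small calculations.

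**1. Are the two monitoring statements consistent?** Yes. Sections 1.8.2 and 4.2.2.1 both give 15 minutes after perflutren. The mismatch is between that period and the cited timing of reactions.

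**2. What do the three 30-minute statements cover?** Two concern cardiopulmonary reactions (sections 1.8.2 and 6.1.1) and one concerns anaphylactoid and other serious reactions (section 1.8.2). All are qualified by most or typically, so 30 minutes is not an outer limit. The hypersensitivity paragraph of section 6.1.1 gives no number of minutes.

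**3. Share of the interval with specified monitoring.** 15 / 30 = 50%, leaving minutes 15 to 30 without it. This is a share of time, not of risk, because the documents give no distribution of onset times.

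**4. Does anything in the protocol support 15 minutes?** Two figures are compatible with it, and neither is offered as the rationale:
- Section 1.8.2 gives an onset of 1 to 15 minutes, but in the paragraph on the 15 pre-market discontinuations. It describes events of moderate intensity that usually resolved untreated, not the serious post-marketing reactions.
- Section 1.8.2 also reports a small pharmacokinetic study (n=8, healthy subjects): mean gas half-life 1.3 minutes, and gas undetectable after 10 minutes in most subjects. This describes clearance of the gas. It does not give the onset time of hypersensitivity.

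**5. Do the exclusions close the gap?** In part. They address cardiopulmonary risk. They cannot address an allergy nobody knows about, and section 6.1.1 notes serious hypersensitivity in people never previously exposed.

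**6. Absolute size.** Inputs: p = 1 to 3 serious events per 10,000 (section 1.8.2); n = 45 (section 4.2.1), of whom 15 are volunteers and 30 are patients (section 1.1). The chance of at least one event is 1 − (1 − p)^n.

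| Group | p = 0.0001 | p = 0.0003 |
|---|---|---|
| All 45 participants | 1 − 0.9999^45 = 0.45% | 1 − 0.9997^45 = 1.34% |
| 30 patients | 1 − 0.9999^30 = 0.30% | 1 − 0.9997^30 = 0.90% |
| 15 volunteers | 1 − 0.9999^15 = 0.15% | 1 − 0.9997^15 = 0.45% |

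These are chances of a serious event at any time. The part falling after 15 minutes would be some unknown fraction of them.

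**The case against.** The strongest defence is that nothing is contradicted. The 30-minute statements describe when reactions happen, and none prescribes an observation period. The mandatory 30-minute period was removed, the label as reported asks only for monitoring without a duration, and the protocol provides monitoring, resuscitation cover and accessible epinephrine. Higher-risk cardiopulmonary patients are excluded and the absolute risk is small. All of this stands, and it rules out calling the 15-minute period a breach. It does not supply a reason for the period, least of all for hypersensitivity.

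A reader might infer four stronger conclusions that the documents do not support:

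- **That half the risk window is unobserved in all 45 participants.** The 30 patients move on to a procedure with staff contact, and trained personnel are available in the clinic (section 4.2.2.1). What is missing is specified reaction monitoring, which is narrower. Half the time is also not half the risk.
- **That volunteers will have left before 30 minutes.** No departure time is stated. The protocol is silent on this, which is the gap, but silence does not show early departure.
- **That the clock is inconsistent, or that scanning uses up the observation period.** Both sections naturally mean time after administration. Section 4.2.2.2 says "Total imaging time is estimated to be less than 15 minutes", so scanning and observation may overlap. However, trained personnel are with the participant during scanning, and the cited interval runs from administration. Details of the contrast agent in section 6 are redacted and cannot be held against the plan.
- **That a later reaction would be lost from the safety record.** Adverse events are recorded through 30 days (sections 8.2 and 8.3.1), charts are followed for 6 months (section 4.2), and causality assessment weighs timing, known side effects and concurrent conditions (section 8.1.2). Late recording does not replace prompt recognition, but the event need not be lost.

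**Conclusion.** The point holds as an unexplained mismatch. Specified monitoring and closing vitals end at 15 minutes, against a protocol-cited interval of 30 minutes for most serious cardiopulmonary reactions and, typically, for anaphylactoid and other serious ones. It matters most for undiagnosed allergy and for the 15 healthy volunteers.

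The absolute risk is low, and the part attributable to minutes 15 to 30 cannot be stated. That places the point below an essential correction, though it bears on participant safety and is cheap to settle.

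Three assumptions apply. The cited composite rate is taken to apply to these participants. The pre-market count of 19 serious cardiopulmonary events in 1,716 subjects is not used, because the protocol describes those events as arising days later and apparently reflecting underlying disease, although it does not rule out a role for the agent. Volunteers are taken to receive perflutren, which their exclusion criteria (section 3.1.2) imply, although section 4.2.2.1 is headed as applying only where applicable.

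**What to change.** Reconcile sections 1.8.2, 4.2.2.1 and 6.1.1. Either the observation period and the closing-vitals time should agree with the interval the protocol cites, or the protocol should state the data that support a shorter period for serious reactions, hypersensitivity included. If the 1 to 15 minute onset figure is to be used for this, the text should say which events it describes.

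State also how the period applies in each arm: for Arm 1, before volunteers leave; for Arms 2 and 3, before the scheduled procedure.

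Which duration is appropriate is for the investigator and IRB to decide. The cost is protocol and consent wording and at most some minutes of nurse time per participant at a single visit. The downside is a slightly longer visit.
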